5.5 Key inclusion criteria

Individuals who are visitors or patients at Pennsylvania Hospital, are identified through the Evolv system as carrying a firearm, and who accept firearm safety materials OR any patient or visitor interested in receiving a firearm storage device who self-selects into the study by scanning the QR code on the study poster. For eligibility of the follow-up survey, participants must have responded yes to taking a cable lock

in the initial brochure survey or yes to receiving a firearm storage device shipped to their address from the poster survey.

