 - i. [LOGIC] Which of the following storage devices would you prefer?
 1. Lock box
 2. Trigger lock
 3. Gun safe
 4. Calmshell / "life jacket"
 5. Gun cabinet
 6. In-vehicle lock
 7. Other/key/PIN/biometric (please specify):
 - c. Don't want to share my address
 - i. [LOGIC] Please select which of the following you'd be open to:
 1. Returning to Penn Medicine to pick up a free cable lock
 2. Receiving a free cable lock locally
 3. Other (please specify)
5. [IF YES #3] What is the best US shipping address for you?
 - a. [Text box fields for street, apt, city, zip, name]
6. How do you usually store your firearm?
 - a. In a locked safe or gun cabinet
 - b. With a trigger lock or cable lock
 - c. Unlocked (not secured with a lock, in a locked container, or not stored in a locked cabinet)
 - d. Other (please specify)
7. Once you receive your cable lock, how likely are you to use it in the next week?
 - a. Extremely likely

- b. Somewhat likely
- c. Neither likely nor unlikely
- d. Somewhat unlikely
- e. Extremely unlikely

Follow-up Survey: Participants who complete the initial survey and who agree to provide contact information will be contacted via text message 1 month after enrollment for a follow-up survey that adds questions about if and how participants have changed their storage behavior. The text language will read:

“Hello, this is Penn Medicine. Thank you for completing our initial survey. If you’re interested in taking the follow-up survey, please click the survey link below: [INSERT LINK]”

Participants will receive the second Amazon gift card incentive 1-2 weeks after completion of this survey. “Hello, this is Penn Medicine. Thank you for participating in our survey. As an appreciation for your time, please see below for your gift card information: [INSERT GIFT CARD #]”

The follow-up survey questions are subject to be amended based on the principal investigators’ discretion. Eligible participants from the initial survey, those who answered yes to accepting a cable lock, will be asked the following questions to understand if their behavior changed:

1. Since you’ve visited Penn Medicine, how have you stored your firearm? [option selection]
 - a. Participants select [a] in a locked safe or gun cabinet, b) with a trigger lock or cable lock, c) unlocked (not secured with a lock, in a locked container, or not stored in a locked cabinet), d) other (please specify) with an open comment box]

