2. Have you used the firearm storage device from Penn Medicine to secure your firearm? [Yes/No]
3. Have you made any other changes in your firearm storage? [write in]

Iterative Analysis and Refinement of Data Collection Methods: We will assess response rates every (1) week and tabulate responses on the acceptability of data collection methods. We will iteratively refine data collection methods over the course of 6 months to achieve the highest possible response rate. The participant data collected will be their phone number and/or their address for individuals completed the survey via the study poster. No identifying information or demographics will be collected to uphold anonymity. Cell phone number will be used to distribute the gift card via the Nudge Unit’s Google Voice account and re-contact with invitation to participate in the follow-up survey. Their address will only be used to ship the firearm storage device to individuals who self-enrolled in the study via the study posters.

9. Analysis plan

The primary outcome is survey response rate. This will be monitored via Qualtrics by looking at response volume by week. These responses will be compared to security department reports on the number of firearms identified/stored to allow us to calculate the proportion of eligible individuals who responded per week. The secondary outcome measures are: (1) firearm storage behavior among a) locked safe/gun cabinet, b) trigger lock or cable lock, c) unsecured, d) other (write in), (2) likelihood of using cable lock within the next week (extremely unlikely to extremely likely scale).

10. Human research protection

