16. 9. wptrace. Missing Pieces. The Trace. Published November 20, 2017. Accessed June 1, 2023. <https://www.thetrace.org/2017/11/stolen-guns-violent-crime-america/>
18. 10. Grossman DC, Mueller BA, Riedy C, et al. Gun storage practices and risk of youth suicide and unintentional

Brief Description for ClinicalTrials.gov

This study aims to enhance workplace safety by implementing a firearm safety program at Penn Medicine's Pennsylvania Hospital. The option to store firearms securely during visits is offered to firearm

owners. The study focuses on understanding barriers and facilitators to this program and piloting methods to collect data on firearm storage device use. The approach prioritizes participant confidentiality and pragmatism. The study design involves iterative pilot testing of data collection methods and comparison of acceptance and usage rates between cable locks and lock boxes through randomization. The intended outcome is to provide evidence supporting the scalability and effectiveness of the program. The study population includes patients and visitors who accept firearm safety materials or express interest in receiving a firearm storage device. The primary outcome measure is survey response rate, with secondary outcomes including firearm storage behavior and likelihood of using a gun safety device. Additionally, the study explores variations in survey distribution methods.

Detailed Description for ClinicalTrials.gov

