This protocol is for Aim 2 and 3 of the study. The rationale for this aim is that traditional research methods for collecting data on firearm safe storage have not been optimized for use in a pragmatic setting to ensure acceptability and confidentiality. Our priority in firearm safety education and device distribution is to get the necessary information and supplies to those who need them. To achieve this, any data collection must be done in a low profile, confidential, and non-threatening way. This is particularly important not only because discussions of firearm ownership can be politically charged, but also because some community members may not be legally licensed to own or carry a firearm, and some may even be legally prohibited from doing so. The legal status of their ownership does not lessen their need for safety information and support—indeed, unlicensed firearm owners may have even fewer safety resources available for them. Our priority is therefore to reach as many individuals as possible while subjecting them to as little scrutiny as possible. Therefore, we aim to design a data collection approach that will prioritize preserving participant confidentiality. Our approach will be iterative pilot tests of data collection methods including embedding unique QR codes linked to surveys in firearm safety brochures and study poster signage. We will offer the opportunity for individuals to take home a cable lock after their visit or to scan the QR code on the brochure/poster to fill out the study survey and get a safety

device shipped to their address. Participants who fill out the study survey will be randomized to receive either a cable lock as the default or a choice between cable lock and lock box to test acceptance and usage rates. For those who accepted a cable lock at the hospital will automatically be grouped in the cable lock default group. The hypothesis we are testing is if iterative pilot testing will reveal a feasible method that balances pragmatism and confidentiality as well as compare acceptance and usage rates among cable locks and lock boxes.

The intended outcome of this study is development of critical evidence to facilitate the scaling of this program to our hospitals and launch a promising research program to study the acceptability, long term use, and cost-effectiveness of a scalable approach to promote safe firearm storage.

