This research study is to design and pilot test a method for collecting data on storage device use among patients and visitors who accept firearm safety materials or are interested in receiving a firearm storage device shipped to their address. The study design is an iterative pilot test of survey data collection methods and determination of scalability and feasibility for distribution of firearm storage devices. The study population and sample will be (a) individuals who are patients or visitors to PAH who are screened for a firearm, screen positive, and accept a firearm safety brochure and storage device OR (b) individuals interested in receiving a firearm storage device and self-scan the unique QR code on the study poster in the entry hall of PAH with minimal or no security supervisor engagement. A unique QR code linking directly to the initial survey will be embedded into the firearm safety brochure as well as the poster in the entry hall of PAH next to the distribution area. Individual group (a) will be informed by security that survey participation is optional, but that it is helpful for our efforts, and that participation will be compensated with a \$10 Amazon gift card for the initial survey and a \$20 Amazon gift card for completing the follow-up survey. Individual group (b) will not be actively engaged by security, and will self-enroll in the study by viewing the posted signage and completing the QR code linked survey. Individuals who decline the device will also be eligible for the initial survey via the poster QR code, but they will not be eligible for the follow-up survey.

The primary outcome measure is survey response rate: whether an eligible visitor or patient completed the firearm storage survey after accepting firearm safety materials or after scanning the QR code on the poster. This will be measured through Qualtrics survey completion rate and PAH Evolv security system foot traffic. We will use the survey completion rate as the numerator and the number of people scanning positive for a firearm as the denominator for this rate.

The secondary outcome measures are from initial and follow-up survey responses: (1) firearm storage behavior, (2) likelihood of using gun safety device within the next week (extremely unlikely to extremely likely scale). These outcomes are directly tied to questions asked in both surveys.

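### Hospital cable-lock acceptors are placed in the default arm without randomisation, which biases the Aim 3 acceptance comparison against the choice arm

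*Protocol*

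**What the plan says.** The randomised comparison appears only in the registry text appended after the references.

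- The Brief Description for ClinicalTrials.gov announces a "comparison of acceptance and usage rates between cable locks and lock boxes through randomization".
- The Detailed Description says that people who fill out the survey are "randomized to receive either a cable lock as the default or a choice between cable lock and lock box to test acceptance and usage rates".
- The next sentence reads: "For those who accepted a cable lock at the hospital will automatically be grouped in the cable lock default group".
- The hypothesis that follows includes the aim to "compare acceptance and usage rates among cable locks and lock boxes".

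Hospital acceptors are also offered the survey. The Detailed Description says "Individual group (a) will be informed by security that survey participation is optional", and group (a) is defined by screening positive and accepting the brochure and device. People who decline the device may still take the initial survey through the poster.

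For usage, the only follow-up schedule described is in section 8.2: participants "will be contacted via text message 1 month after enrollment for a follow-up survey", which asks "Have you used the firearm storage device from Penn Medicine to secure your firearm". Section 5.5 restricts who receives it: "For eligibility of the follow-up survey, participants must have responded yes to taking a cable lock" in the brochure survey, or yes to a shipped device in the poster survey.

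Nothing in the protocol keeps the automatically grouped people out of the arm comparison. Section 9 does not mention that comparison.

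**The concern.** Acceptance is one of the two outcomes of the comparison, and under this rule having accepted decides arm membership. A hospital acceptor can only be in the default group. A hospital decliner who completes the poster survey can be randomised to either. The default arm therefore receives a block of people with acceptance fixed at 1, and the choice arm receives no counterpart. Randomisation no longer protects the contrast, although the Brief Description presents it as randomised.

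Usage is affected differently. Hospital acceptors are confirmed firearm carriers who hold the lock from the day of the visit. Poster participants select themselves and must wait for shipping. A question asked one month after enrollment then covers different periods of possession in different people.

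At stake is the Aim 3 question of how lock boxes compare with cable locks in acceptance and usage. Section 4 (Background) names randomised trials of lockboxes as a long-term goal, so a biased pilot estimate could misdirect that work.

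**Working it through.** The protocol states no sample size, allocation ratio, effect or analysis for this comparison, so there is no figure to reproduce. The bias can be derived directly.

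**Formula.** Let n people be randomised to each arm and h hospital acceptors be added to the default group. Let pc be acceptance among randomised default participants and d the true difference (choice minus default).

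- Pooled default acceptance = (n·pc + h)/(n + h)
- Observed difference = pc + d − (n·pc + h)/(n + h) = d − w(1 − pc), with w = h/(n + h)

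The term w(1 − pc) is positive whenever w > 0 and pc < 1, and it is never negative. The bias therefore runs against choice and cannot reverse.

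**Inputs, all assumed.** n = 50 per arm and d = +13 points. pc = 47%, borrowed from the in-person acceptance rate in the Detailed Description; 65%; or 80%, because poster respondents are already interested in a device.

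**Example.** With pc = 47% and h = 50, pooled default acceptance = (23.5 + 50)/100 = 73.5%. Choice acceptance is 47 + 13 = 60%. The observed difference is −13.5 points.

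| Acceptors added (h) | pc = 47% | pc = 65% | pc = 80% |
|---|---|---|---|
| 10 | +4.2 | +7.2 | +9.7 |
| 25 | −4.7 | +1.3 | +6.3 |
| 50 | −13.5 | −4.5 | +3.0 |
| 100 | −22.3 | −10.3 | −0.3 |

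Entries are the observed difference in points when the truth is +13.

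**Point at which the effect disappears.** h = n·d/(1 − pc − d):

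- pc = 47%: 6.5/0.40 = 16.25
- pc = 65%: 6.5/0.22 = 29.5
- pc = 80%: 6.5/0.07 = 92.9

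Per randomised default participant that is 0.33, 0.59 and 1.86 acceptors.

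**No true effect (d = 0), h = 50.** −0.5(1 − pc) = −26.5, −17.5 and −10 points.

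**Second parameterisation as a check.** Let f be the share of everyone analysed who accepted at the hospital, with the rest randomised 1:1 (assumed) and true acceptance p in both arms. Then w = 2f/(1 + f), and the spurious gap is (1 − p)·2f/(1 + f). With p = 47%:

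| f | Default, observed | Choice | Spurious gap | Approx. chance of a false significant result, 200 people |
|---|---|---|---|---|
| 0.10 | 56.6% | 47% | 9.6 points | 27% |
| 0.25 | 68.2% | 47% | 21.2 points | 84% |
| 0.47 | 80.9% | 47% | 33.9 points | 99.5% |

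The last column assumes a two-sided 5% test and 200 people in total. Over p = 30% to 90% and f = 0.10 to 0.60 the gap runs from 1.8 to 52.5 points, always favouring default.

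**After the fix.** With only randomised people compared, w = 0 and the bias is zero for every pc.

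**Usage.** With f = 0.25 and usage of 50% among randomised people, default-group usage becomes 42%, 50% or 58% if hospital acceptors use the lock at 30%, 50% or 70% (all assumed). The direction depends on a rate the protocol does not give.

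**The case against.** The strongest reply is that grouping people is not the same as pooling them in an analysis. The sentence could be operational, meaning only that someone who already holds a cable lock is not offered the choice, and the SAP, which is not at hand, could define the analysis set. This does not clear the text. The group named is the randomised arm defined one sentence earlier, the next sentence restates the comparison, and nothing removes these people from it. An SAP that excluded them would depart from the stated allocation rule.

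Second, the comparison is peripheral here. The Abstract limits the protocol to Aim 2, section 5.2 schedules a separate IRB approval for Aim 3, and the registry outcomes include no between-arm acceptance or usage endpoint. That limits the severity. But the Detailed Description says it covers Aims 2 and 3, and it is where the randomised design is set out.

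Third, the figures are illustrative. The +13 points has no source, the 47% comes from a different setting, and pc could exceed 80%. This stands. At pc = 95% with w = 0.5 the spurious gap is only 0.5 × 0.05 = 2.5 points, and at 100% it is zero. The direction is secure; the size is not.

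Fourth, the usage argument joins the Aim 2 follow-up survey to the Aim 3 comparison, section 8.2 allows its questions to change, and no shipping time is given. Usage is therefore a secondary point.

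**Conclusion.** The concern holds and should be fixed. The stated rule makes default-arm membership depend on the outcome. If the groups are compared as written, acceptance in the default group is inflated by w(1 − pc) whenever any hospital acceptors are included and acceptance among randomised default participants is below 100%.

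The direction follows from the text. The size rests on assumed inputs and ranges from negligible, when nearly all randomised people accept, to large enough to reverse a real advantage for choice. Hospital acceptors are unlikely to be few: the Detailed Description reports more than 400 locks and brochures already distributed. Usage is confounded in an unknown direction. The damage is confined to the Aim 3 comparison.

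**What to change.** Replace the automatic-grouping sentence with one stating that people who accepted a cable lock at the hospital are not randomised, are reported as a separate descriptive cohort, and are excluded from the arm comparison. Compare only randomised participants, by assigned offer (default or choice), with everyone randomised in the denominator. Carry a randomised yes/no flag in the dataset.

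Two secondary points can be settled in the same edit:

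- **Usage denominator.** Non-acceptors are not eligible for the follow-up survey under section 5.5. One option is to count them as non-users of the study device, which is an estimand choice to state explicitly. A rule is also needed for acceptors who skip the optional follow-up.
- **Device received.** Label any cable-lock versus lock-box comparison by device received as observational.

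The text change is one sentence and one data field, and it alters nobody's device. The real costs are a smaller default group and narrower applicability: the randomised contrast would rest mainly on poster self-selectors and people who declined a lock at the hospital, so it would say less about screened carriers who accept one on site.
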